Table 2 Schedule of activities for patients who have discontinued study drug or completed treatment with study drug

Evaluation	Time since last dose of durvalumab								For details, see Section	
	Day (± 3)	Months (± 1 week)						12 months and every 3 months (± 2 weeks)		
	30	2	3	4	6	8	10			
Physical examination (full)	X								8.2.2	
Vital signs	X								8.2.3	
Body weight	X	X	X						8.2.3	
Pregnancy test ^a	X	As clinically indicated							8.2.1	
AE/SAE assessment	X	X	X						8.3	
Concomitant medications	X	X	X						6.4	
WHO/ECOG PS ^b	At timepoints consistent with tumor assessments; at 30, 60, and 90 days after last dose; and then at initiation of subsequent anticancer therapy								8.2.6	
Subsequent anticancer therapy ^{c,d}	← →									
Survival status ^e		X	X	X	X	X	X		8.1.1	
Hematology	X	X	X						8.2.1	
Clinical chemistry	X	X	X						8.2.1	
Urinalysis	As clinically indicated								8.2.1	
TSH (reflex free T3 or free T4) ^f	X	X	X						8.2.1	
CCI [REDACTED]		X	X	X					8.1.2.1, 8.1.2.2, 8.1.2.3, 9.5.2.3	
Tumor assessment as per local institutional standard care (RECIST 1.1) ^h	Additional scans to be completed per standard practice post progression. Patients who permanently discontinue IP for reasons other than objective RECIST 1.1 disease progression should continue to have RECIST 1.1 assessments performed q8w \pm 1 week beginning 8 weeks after IP treatment initiation for the first 48 weeks (relative to the first dose) and q12w \pm 1 week thereafter until clinical progression/deterioration or RECIST 1.1-defined radiological progression plus one or more additional follow-up scans for confirmation of progression until confirmed radiological progression, the end of study, death, study discontinuation, or Sponsor decision (whichever comes first).								8.1, Appendix F	

AE = Adverse event; CT = Computed tomography; eCRF = Electronic case report form; CCI [REDACTED]

CCI

= Investigational product; IV = Intravenous; MRI = Magnetic resonance imaging; NSCLC = Non-small cell lung cancer; PD = Progressive disease; **CCI** [REDACTED]; IP

CCI

CCI [REDACTED]; q8w, q12w = Every 8, 12 weeks, respectively; RECIST 1.1 = Response Evaluation Criteria in Solid Tumors version 1.1; SAE = Serious adverse event; T3 = Triiodothyronine; T4 = Thyroxine; TSH = Thyroid-stimulating hormone; WHO/ECOG PS = World Health Organization/Eastern Cooperative Oncology Group Performance Status.

- ^a For women of childbearing potential only. A urine or serum pregnancy test is acceptable.

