During the treatment period, patients who are clinically stable at an initial RECIST 1.1-defined progressive disease (PD) may continue to receive study treatment at the discretion of the Investigator and patient. A follow-up scan is to be collected after the initial RECIST 1.1-defined PD, preferably at the next (and no later than the next) scheduled imaging visit, and no less than 4 weeks after the prior assessment of PD; this follow-up scan is evaluated using the Confirmation of Radiological Progression criteria. Patients with confirmed PD who continue to receive durvalumab at the discretion of the Investigator and patient (following consultation with AstraZeneca) can receive treatment for the remainder of the 12-month treatment period, and tumor assessments should continue on their regular imaging schedule for the duration of treatment.

Follow-up of patients after discontinuation of study drug

Patients who have discontinued study treatment due to toxicity or symptomatic deterioration, clinical progression, or who have commenced subsequent anticancer therapy, will be followed up for adverse events (AEs) and with PRO-questionnaires for 90 days after investigational product (IP) discontinuation, and thereafter followed up with tumor assessments until

RECIST 1.1-defined radiological PD plus an additional follow-up scan or until death (whichever comes first).

Survival

All patients in the study should be followed up for survival at months 2, 3, 4, 6, 8, 10, and 12 following treatment discontinuation or completion, and then every 12 weeks until death, withdrawal of consent, or the end of the study, as per the SoA.

Steering Committee

If required, a Steering Committee (SC) will be assembled by AstraZeneca for the executive oversight and supervision of the study. The SC will consist of oncology experts and a statistician who serve their role through regular scheduled meetings or teleconferences and, if necessary, additional ad hoc meetings. Details of the SC remit, procedures, processes, and meeting frequency will be outlined in an SC Charter.

Interim analysis

No formal interim analyses are planned for this study.

Statistical methods

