4 STUDY DESIGN

4.1 Overall design

This is a Phase II open-label, single-arm, multicenter, international study to evaluate the clinical activity of durvalumab (1500 mg q4w) in patients with Stage III unresectable NSCLC who have an Eastern Cooperative Oncology Group (ECOG) PS of 0 to 2 and who were treated with radiotherapy but are ineligible for chemotherapy. Patients will be enrolled into 2 cohorts according to the dose of radiotherapy received prior to study entry (Cohort A: Standard Radiotherapy [60 Gy \pm 10% or hypofractionated BED]; Cohort B: Palliative Radiotherapy [40 to < 54 Gy or hypofractionated BED]).

Approximately 150 patients will be treated with the study drug in Europe and North America. Patients will be in CR, PR, or have SD following radiation therapy, as assessed by the Investigator and further supported by the screening imaging radiological assessment. Patients must not have progressed following radiation therapy, and radiation therapy must be completed within 6 weeks (42 days) prior to first IP dose administration. The last dose of radiation therapy is defined as the day of the last radiation treatment session.

Patients must have histologically- or cytologically-documented NSCLC and locally-advanced, unresectable Stage III disease (according to the International Association for the Study of Lung Cancer [IASLC] Staging Manual Version 8 [\[IASLC 2016\]](#)). Patients must be deemed to be ineligible for chemotherapy per Investigator assessment.

For an overview of the study design see [Figure 1](#), Section [1.3](#). For details on treatments given during the study, see Section [6.1](#) Treatments Administered.

For details on what is included in the efficacy and safety endpoints, see Section 3 Objectives and Endpoints.

Patients will receive study treatment for 12 months or until RECIST 1.1-defined radiological progression by Investigator unless there is evidence of an unacceptable toxicity, or if the patient requests to stop the study treatment. See Section 6.1.3 for detailed criteria.

Patients who have discontinued study treatment due to toxicity or symptomatic deterioration, clinical progression, or who have commenced subsequent anticancer therapy, will be followed up for AEs and with PRO-questionnaires for 90 days after study treatment discontinuation, and thereafter followed up with tumor assessments until RECIST 1.1-defined radiological PD plus an additional follow-up scan or until death (whichever comes first).

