- Patient agrees to re-consenting to be treated through progression.

Patients will not be permitted to continue treatment with durvalumab if progression occurs after confirmed response (CR or PR as defined by RECIST 1.1) in the TLs (regardless of the appearance of new lesions) (ie, the response and progression events both occurred in the TL while receiving durvalumab).

Patients who AstraZeneca and the Investigator determine may not continue treatment after RECIST 1.1-defined PD will be followed up for survival. Patients who have discontinued treatment due to toxicity or symptomatic deterioration, or who have commenced subsequent anticancer therapy, will be followed up with tumor assessments until RECIST 1.1-defined PD plus an additional follow-up scan or until death (whichever comes first) and followed for survival (refer to Section 7.1.2).

Treatment after final overall survival data cutoff

At the time of the DCO, the analysis portion of the clinical study will have been completed and all patients remaining in the study will be considered to have completed the analysis portion of the study. At the time of DCO, the clinical study database will be closed to new data.

Patients in OS follow-up (progressed and have discontinued treatment) will be considered to have completed the study.

Patients who are receiving treatment at the time of DCO may continue receiving IP until 12 months if the Investigator judges that they are gaining clinical benefit.

All patients will receive efficacy scans and follow-up care in accordance with standard local clinical practice. Data should be recorded on patient charts but will not otherwise be reported for the purposes of this study.

For patients who are continuing to receive treatment with durvalumab following the final DCO and database closure, it is recommended that the patients continue the scheduled site visits and Investigators monitor the patients' safety laboratory results prior to and periodically during treatment with durvalumab in order to manage AEs in accordance with the durvalumab Dosing Modification and Toxicity Management Guidelines (see Section 8.4.5.1).

Following the DCO, SAE reporting applies only to patients who are active on IP and within 90 days after the last dose; in all other cases, only a Statement of Death notification is to be sent to AstraZeneca. No OS data will be recorded in the study database after DCO for the study.

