7.1.1 Follow-up of patients post discontinuation of study treatment

All patients who discontinue the study treatment will be followed up for safety assessments (AEs) and with CCI 90 days after their last dose of study treatment and for

survival follow-up. Additional assessments to be performed at the time of the 90-day safety follow-up are detailed in the SoA ([Table 2](#)).

Patients who have discontinued study treatment prior to objective RECIST 1.1-defined radiological progression will be followed up with tumor assessments according to the SoA ([Table 2](#)) until RECIST 1.1-defined PD or death, regardless of whether or not the patient started a subsequent anticancer therapy, unless they have withdrawn all consent to study-related assessments.

Subsequent anticancer therapy (including radiation therapy) will be assessed and recorded from the end of treatment with study treatment through the safety and survival follow-up period or until death for patients who have discontinued study treatment, including at PD.

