7.1.3 Procedures for discontinuation of study treatment

Discontinuation of study treatment, for any reason, does not impact the patient's participation in the study. A patient who decides to discontinue IP will always be asked about the reason(s) for discontinuation and the presence of any AE. The patient should continue attending subsequent study visits, and data collection should continue according to the study protocol. If the patient does not agree to continue in-person study visits, a modified follow-up must be arranged to ensure the collection of endpoints and safety information. This follow-up could be a telephone contact with the patient, a contact with a relative or treating physician, or information from medical records. The approach taken should be recorded in the medical records. A patient that agrees to modified follow-up is not considered to have withdrawn consent or to have withdrawn from the study.

Patients who are permanently discontinued from further receipt of IP, regardless of the reason, will be identified as having permanently discontinued treatment. Patients who are permanently discontinued will enter follow-up (see the SoAs in [Table 1](#) and [Table 2](#)).

Patients who permanently discontinue drug for reasons other than objective RECIST disease progression should continue to have RECIST scans performed every 8 weeks (q8w) \pm 1 w for the first 48 weeks (relative to the date of the first dose), and then every 12 weeks \pm 1 w thereafter until RECIST 1.1-defined radiological PD plus an additional follow-up scan or death (whichever comes first) as defined the SoAs ([Table 1](#) and [Table 2](#)).

If a patient is discontinued for RECIST 1.1-defined progression, then the patient should have 1 additional follow-up scan performed preferably at the next (and no later than the next) scheduled imaging visit, and no less than 4 weeks after the prior assessment of PD.

All patients will be followed for survival until the end of the study.

Patients who decline to return to the site for evaluations should be contacted by telephone as indicated in the SoAs ([Table 1](#) and [Table 2](#)) as an alternative.

Patients who have permanently discontinued from further receipt of IP will need to be discontinued from the IVRS/IWRS.

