#### **3.3.1 Progression-Free Survival**

Progression-free survival is defined as the time from the date of first dose of durvalumab until the date of objective disease progression or death (by any cause in the absence of progression) regardless of whether the patient discontinues durvalumab or receives another anticancer therapy prior to progression.

- $PFS \text{ (days)} = (\text{date of PFS event or censoring}) - (\text{date of first dose of durvalumab}) + 1$ .

Patients who have not progressed or died at the time of analysis will be censored at the date of their last evaluable tumor assessment (ie, this doesn't include NE or missing value).

If the patient progresses or dies after 2 or more missed visits, the patient will be censored at the date of the latest evaluable assessment prior to the missed visits.

If the patient has no evaluable visits or does not have baseline data, he/she will be censored at Day 1 unless he/she dies within 2 visits of baseline, in which case the date of death is the event date.

Given the scheduled visit assessment scheme (i.e. eight-weekly for the first 48 weeks then twelve-weekly thereafter) the definition of 2 missed visits will change.

1. If the previous RECIST assessment is baseline then two missing visits will equate to 17 weeks since the previous RECIST assessment, allowing for a late visit (i.e.  $2 \times 8$  weeks + 1 week for a late assessment = 17 weeks).
2. If the previous RECIST assessment is post baseline and less than study day 274 (i.e. week 39) then two missing visits will equate to 18 weeks since the previous RECIST assessment, allowing for early and late visits (i.e.  $2 \times 8$  weeks + 1 week for an early assessment + 1 week for a late assessment = 18 weeks).
3. If the two missed visits occur over the period when the scheduled frequency of RECIST assessments changes from eight-weekly to twelve-weekly this will equate to 22 weeks (i.e. take the average of 8 and 12 weeks which gives 10 weeks and then apply same rationale, hence  $2 \times 10$  weeks + 1 week for an early assessment + 1 week for a late assessment = 22 weeks). The time period for the previous RECIST assessment will be from study days 274 to 344 (i.e. week 39 to week 49).
4. From week 49 onwards (when the scheduling changes to twelve-weekly assessments), two missing visits will equate to 26 weeks (i.e.  $2 \times 12$  weeks + 1 week for an early assessment + 1 week for a late assessment = 26 weeks).

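### The synopsis and Section 4.1 can be read as starting tumour assessments only after the 90-day safety follow-up, and Table 2 ends them at clinical progression; both conflict with the continuous schedule that PFS needs

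*Protocol*

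**What the plan says.** The passages fall into three groups.

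**Summary text with a 90-day step.** The synopsis (follow-up after discontinuation of study drug) covers patients who stop for toxicity, symptomatic deterioration or clinical progression, or who have started another anticancer therapy. They are followed for AEs and questionnaires "for 90 days after investigational product (IP) discontinuation, and thereafter followed up with tumor assessments until" RECIST 1.1 progression plus one further scan, or death. Section 4.1 repeats the order: "for 90 days after study treatment discontinuation, and thereafter followed up with tumor assessments until RECIST 1.1-defined radiological PD".

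**Operative text without that step.**
- Section 7.1.3: "Patients who permanently discontinue drug for reasons other than objective RECIST disease progression should continue to have RECIST scans performed every 8 weeks (q8w" ± 1 week) to Week 48 from first dose, then every 12 weeks, until RECIST 1.1 progression plus one scan, or death.
- Section 7.1.1: patients who stop before radiological progression "will be followed up with tumor assessments according to the SoA" in Table 2, until RECIST 1.1 progression or death, whether or not they start another therapy.
- Section 6.1.3: patients stopping for toxicity or deterioration, or starting another therapy, "will be followed up with tumor assessments until RECIST 1.1-defined PD plus an additional follow-up scan or until death".
- Appendix F and SAP 3.1.1.2: patients with symptomatic deterioration go on being scanned where feasible.

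**Table 2.** Patients who stop for reasons other than RECIST progression "should continue to have RECIST 1.1 assessments performed q8w" and later every 12 weeks, with no pause. However, the same row gives clinical progression or deterioration as one of the points at which this ends.

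For the analysis, SAP 3.3.1 says: "If the patient progresses or dies after 2 or more missed visits, the patient will be censored" at the last evaluable scan before the gap. It sets two missed visits at 17, 18, 22 or 26 weeks, depending on the date of the previous scan.

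**The concern.** PFS is defined to count progression or death regardless of whether the patient stops durvalumab or starts another therapy. That works only if scanning carries on after stopping. The patients named in the synopsis and Section 4.1 are a group in whom early progression is plausible. If a site acts on the summary sentence, their progression is found late, or the gap becomes long enough for the missed-visit rule to apply.

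That rule depends on outcome. A patient who progresses or dies after the gap is censored back at the earlier scan. A patient scanned after the same gap without progression keeps the full time. Late dating and this form of censoring both push PFS upward, even if stopping carries no added risk. DoR takes its end date from PFS and inherits the problem.

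The Table 2 stopping wording has a related effect. If scans end at clinical progression or deterioration, a later radiological progression in those patients is never observed.

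**Working it through.** **Inputs.** Scans at Weeks 8, 16, 24, 32, 40 and 48, then every 12 weeks (Table 1, Table 2, Section 7.1.3). Pause of 90 days (literal reading of the synopsis and Section 4.1). Missed-visit limits from SAP 3.3.1. Baseline scan 0 to 28 days before first dose (Table 1, footnote u).

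**The SAP's own limits reproduce.** 2×8+1 = 17 weeks; 2×8+1+1 = 18; 2×10+1+1 = 22; 2×12+1+1 = 26. Day 274 = 39×7+1 and day 344 = 49×7+1.

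**Scans skipped.** 90/56 = 1.6 intervals in the 8-weekly phase, so one or two.

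**Consequence by stopping day.** Each day is counted once. The next scan is the first scheduled one after the pause, done on its nominal day.

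| Stopping time | Scans skipped | Days | Gap between scans | SAP limit | Progression at next scan |
|---|---|---|---|---|---|
| Weeks 8 to <40 | 1 | 88 of 224 (39%) | 16 weeks | 18 | event, dated late |
| Weeks 8 to <40 | 2 | 136 of 224 (61%) | 24 or 28 weeks | 18 | censored |
| Weeks 40 to <48 | 1 | 50 of 56 | 20 weeks | 22 | event, dated late |
| Weeks 40 to <48 | 2 | 6 of 56 | 32 weeks | 22 | censored |
| Before Week 8 | 1 | 22 of 56 | 16 weeks + baseline lead | 17 | censored only if baseline scan was more than 7 days before first dose |
| Before Week 8 | 2 | 34 of 56 | 24 weeks + baseline lead | 17 | censored |

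With one scan skipped, the delay is up to 8 weeks, or 12 weeks around Week 48. A stop at Week 48 itself is an exception: one scan is skipped, but the gap from Week 48 to Week 72 is 24 weeks against a limit of 22, so progression is censored.

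**Sensitivity of the 61%.** Let t be days from the last scan to stopping (0 to 55), with a post-baseline last scan in the 8-weekly phase and a limit of 126 days.
- Nominal scan days: the day-112 scan falls inside the pause when t+90 ≥ 112, so t ≥ 22, or 34/56 = 61%.
- Late end of the ±1 week window used: that scan can be done on day 119, so it is lost only when t+90 ≥ 119, so t ≥ 29, or 27/56 = 48%.
- Scan on day 91 after stopping: the gap is t+91, above 126 when t ≥ 36, or 20/56 = 36%.

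**On the dosing calendar.** An on-time last dose falls 0 or 28 days after a scan. Counting the 90 days from last dose, Weeks 8, 16, 24 and 32 skip one scan and progression is kept. Weeks 12, 20, 28 and 36 skip two and it is censored, unless the scan is done at the very end of its window (28+90 = 118, window closes on day 119).

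**With scans continued.** The largest gap in the 8-weekly phase is 8+2 = 10 weeks, below 18. No progression is censored for this reason.

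**The case against.** A reader might infer that the protocol halts scanning for 90 days and that the SAP then censors these patients' progression as a rule. The documents support neither statement.

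- Neither summary sentence says that scans stop. *Thereafter* may only mark the end of AE and questionnaire collection. Section 8 makes adherence to the schedule of activities a requirement, and the operative sections give the interval that the summary sentence lacks. A site following them would miss nothing. This stands: it is an ambiguity, not evidence that scans were missed.
- Censoring is not general. On nominal dates, 39% of stopping times in Weeks 8 to 40 lose one scan and the progression still counts. The 61% also falls to 48% or 36% under reasonable scan timing. This stands.
- The effect on PFS12 cannot be taken from the documents. They give no median PFS, stopping rate or hazard after stopping for this trial. Section 2.3.2.1 reports only that about 10% stopped for an AE in other monotherapy studies. Simulation with assumed inputs (median 6 or 9 months, 10% to 30% stopping before progression, hazard after stopping 1 to 3 times, every site pausing) moves PFS12 by 0 to 4 points. That is an illustration. For scale, the 95% half-width for a proportion near 38% with 102 patients is 1.96×√(0.38×0.62/102) ≈ 9 points.
- PFS and DoR are secondary and descriptive. This stands and limits the weight of the point.

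The objection does not remove the contradiction itself, or the second one within Table 2. Pointing readers to Table 2 is not enough, because its row can be read as ending scans in two of the groups named in the synopsis.

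**Conclusion.** The point holds as an inconsistency that should be reconciled. The synopsis and Section 4.1 can be read as deferring tumour assessments by 90 days, against Sections 6.1.3, 7.1.1 and 7.1.3, Table 2, Appendix F and SAP 3.1.1.2. Table 2's ending at clinical progression or deterioration conflicts with the synopsis and Sections 4.1, 7.1.1 and 7.1.3, which continue to RECIST 1.1 progression or death.

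If the pause were followed, progression at the next scan would be censored for roughly 36% to 61% of stopping times in Weeks 8 to 40 and otherwise usually dated late. These percentages treat stopping days as equally likely and describe stopping times, not patients. The direction for PFS, PFS6, PFS12 and DoR is upward; the size cannot be computed from the documents. The primary endpoint of Grade 3 and 4 PRAEs within 6 months is not touched.

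**What to change.** 1. In the synopsis and Section 4.1, state that the 90-day AE and questionnaire follow-up runs in parallel with tumour assessments, which continue on the first-dose schedule already in Section 7.1.3 (every 8 weeks to Week 48, then every 12 weeks).
2. Reconcile the stopping wording in Table 2 with the synopsis and Sections 4.1, 7.1.1 and 7.1.3. The sponsor has to settle which end point for scanning applies to patients with clinical progression or deterioration and use it throughout.
3. Before database lock, list discontinued patients without RECIST progression who have no scan in the 90 days after stopping, and query each one. This works even if it is too late to amend the protocol.

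Cost: one sentence in two places, one table row and one data-management listing. Step 1 adds no scans beyond those in Section 7.1.3. Relative to Table 2 as written, it may add some for patients with clinical progression or deterioration, depending on how step 2 is settled.
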